4.8 Qualitative study

User experience on removable walker boot will be explored through semi-structured walking interviews. A random sample of patients in the intervention arm of the trial, stratified by gender and age group, will be sampled. Recruitment will be undertaken when the participant joins the trial. The walking interview will be arranged for 2-4 weeks after they receive the walker boots to allow time for the interviewee to experience living with the walker boot. We will recruit until data saturation – estimate fifteen patients from each site. The researcher will arrange to spend up to half a day with each patient. They will be asked to show the researcher around their household and locality as far as they are able to reach without transport and during this walk, explain how use or not of the device affects their ability to undertake daily routines and mobility. They will be asked about their experiences of using the device, challenges they meet in using the device and how they negotiate challenges related to using removable walker boots. They will also be asked about what modifications can be made to improve its effectiveness in off-loading at the same time as to improve adherence. The researcher will audio record the interview and take field notes. Interviews will be transcribed and translated. Fieldnotes will be typed up and

expanded after the walking interview. Data from all sites will be combined for thematic analysis, whilst paying attention to differences in context for interviewees from the different sites.

4.9 Trial analysis plan

The adherence to off-loading devices in the intervention will be based on the number of steps taken by the patient during the assessment period. The mean cumulative steps taken (confidence limits) will be measured using the foot device. We will also measure and compare the difference between wrist and foot between intervention and control. The mean user satisfaction score between the intervention and control group will be tested using t-test. Higher the user satisfaction score indicates greater the satisfaction with the off-loading device. The healing rate between the groups as percentage reduction in the ulcer area per unit time (8 weeks) will be compared between the two groups using methods we have used before. Our statistical philosophy is based on observed standards and confidence/credible intervals and not on hypothesis testing.(34)

5 Governance, Ethics, data collection and security

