2.3 Current use of off-loading methods to heal plantar ulcers in LMICs

Studies in high income countries show adherence with removable off-loading devices ranging from 28% to 60% (≥80% of daily steps/time) .(22) The situation may be very different in low and middle income countries (LMIC).

We conducted a literature review with the aim of understanding the effectiveness of total contact casts compared to removable off-loading devices for plantar ulcers in patients with diabetes mellitus or leprosy in LMIC. We sought to understand the predictors of adherence to using off-loading devices to heal plantar ulcers to diabetes mellitus or leprosy and any difference in healing rates. Our database search yielded 250 potentially relevant abstracts. These abstracts were reviewed by two researchers. We included 8 studies in the review, 5 randomized control trials; and 3 case series. The majority of the studies identified focused on people with diabetes (n=6)(23, 24, 25, 26, 27, 28) and only one study focused on people affected by leprosy (29) . The final study, a case series,1 included a mixed population of people affected by leprosy, diabetes and meningomyelocele.(30) The majority of the studies (n=5)

used total contact cast (25, 27, 30, 31, 32) as off-loading method and found it to be superior to other techniques (modified ankle foot orthosis (26), removable ankle high cast, (33) and standard dressing (25, 32). Adherence to cast use has been reported to be a major concern but none of the studies measured adherence objectively.(25, 26, 27, 29, 30) None of the studies used removable off-loading devices of the type we propose to test in this study. As a result of difficulties in procurement and support, the great majority of people in LMICs with neuropathic ulcers receive none of the above devices and are provided with footwear with a soft insole of Micro-cellular rubber.

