4.4 Sample size

We will include 150 people with neuropathic ulcers due to leprosy and diabetes in the study (75 each from India and Nepal). If adherence is 0.5 (50%) then the 95% CIs (n=150) would be 0.42 to 0.58. Any other proportion would provide narrower CIs. We do not anticipate observing a difference in ulcer healing between intervention and control because, given a control healing rate of 70%, the intervention group would have to be 90% to have a 80% power.

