4.6.3 Randomization and allocation

Participants will be enrolled sequentially, and randomly allocated (1:1) to receive removable walker boot or MCR using the "digital sealed envelope" method resident in a computer. An allocation table will be generated remotely by the trial statistician at the George Institute of Global Health India. A permuted block random method will be used to generate the randomization sequence within each stratum.

Randomly selected blocks of size 2, 4, 6, or 8 will be generated to maintain balance between the numbers allocated to each of the two groups and to ensure allocation concealment. The generated table will be uploaded into the REDCap software to be used for participant enrolment. Access to the allocation table will be restricted. Trial staff in India and Nepal will not have access to the allocation table. When a participant's details are submitted, the trial arm and a unique study number will be assigned and revealed to the local clinician so that the randomized group that the participant is assigned to cannot be

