4.6.5 Main outcome measures

- 1. Adherence to removable walker boot: Adherence will be measured using pedometer; one placed inside the walker boot and second on patient's wrists as a watch/ in pocket. The pedometer will provide data on number of steps taken by patient during the assessment period which will be recorded weekly. We will compare the groups based on their steps per day. In addition, the difference in cumulative steps recorded between the two pedometers will provide a further measure the compliance to walker boot. We will measure the difference in the difference between intervention and control.
- User satisfaction: We will measure the user satisfaction with the off-loading devices using the Quebec User Evaluation of Satisfaction with Assistive Technology (QUEST) 2.0 at complete healing of ulcer or at 8 weeks from recruitment, whichever is earlier.
- 3. Ulcer healing: We will measure the healing of ulcer time to (complete epithelisation of ulcer) and also measure the rate of healing. All observations will be based on 'blind' assessment. The patient will be followed up for 8 weeks and photographs of ulcers will be taken at baseline and after every 2 weeks until the ulcer heals or at 8 weeks, whichever is earlier, to measure the ulcer area. The ulcer will be measured from the photographs taken using the data collection tablets. The ulcer will

altered.

be measured by masked observers in another site using the PUSH (Pressure Ulcer Scale for Healing) tool with which we have considerable experience.

The photographs of the ulcer will be taken using standard and uniform method in both the study sites. Photographs will be taken in a well-lit area in a long sitting position with the foot elevated slightly on soft material. The image of the ulcer will be captured by the research assistant standing directly in front of the patient with the camera placed parallel to the affected foot/ulcer.

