4.7 Follow-up and study end points

Patients will be followed up weekly for 8 weeks or until ulcer completely heals, whichever is earlier. The complete healing of ulcer will be determined clinically as complete closure of epithelium of the skin which will be photographed for verification. In the event that study participants develop any complications such as worsening of existing ulcer, skin abrasions due to friction or sever swelling to the foot or leg, they may be considered as censored if it affects the wearing of the off-loading device and will not be continued for follow-up. Such patients will be referred to The Leprosy Mission Trust India tertiary hospital at Champa in India and Anandaban Hospital in Nepal for further evaluation and treatment.

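### Adherence is sized as a proportion but analysed as step counts and a raw step difference, which are not adherence rates and move with walking volume and, for the cumulative measures, with days observed

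*Protocol*

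**What the plan says.** Sections 1.2 and 3 of the Protocol put adherence rates, device versus standard care, first among the primary objectives. Section 4.4 sizes the trial on a proportion: "If adherence is 0.5 (50%) then the 95% CIs (n=150) would be 0.42 to 0.58". The 150 are everyone randomised; section 4.6.3 has them "randomly allocated (1:1) to receive removable walker boot or MCR".

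The background in section 2.3 also treats adherence as a share, citing studies from high-income countries with "adherence with removable off-loading devices ranging from 28% to 60% (≥80% of daily steps/time".

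The analysed quantities differ. Section 4.9 bases adherence on the number of steps: "The mean cumulative steps taken (confidence limits) will be measured using the foot device", together with a comparison between arms of the wrist-foot difference. Section 4.6.5 compares the groups on steps per day, without saying from which pedometer, and adds that "the difference in cumulative steps recorded between the two pedometers will provide a further measure the compliance to walker boot". No section divides device steps by total steps.

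Observation time varies. Under section 4.7, "Patients will be followed up weekly for 8 weeks or until ulcer completely heals, whichever is earlier", and some complications can also end follow-up. Both pedometers are read weekly, and the form in Appendix 3 has a row for each.

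**The concern.** The quantity sized and the quantities analysed are different things. A mean step count or a mean step gap cannot be set against an interval of 0.42 to 0.58, or against literature that reports a percentage of adherent people.

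The step measures also respond to things other than wearing the device. Someone who walks a lot accumulates many device steps and a large gap, whatever share of walking is done in the device. Someone who heals early accumulates fewer of both. On the first measure early healing looks like poor adherence, and on the second it looks like good adherence.

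At stake is the trial's first feasibility result. A larger trial would be planned from a figure that mixes adherence with activity and healing time.

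**Working it through.** **The plan's own figure.** Inputs from 4.4: p = 0.5, n = 150. The Wald interval is p ± 1.96 × √(p(1−p)/n) = 0.5 ± 1.96 × √(0.25/150) = 0.5 ± 0.080, that is 0.42 to 0.58. The stated interval reproduces. It pools both arms.

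**One arm.** With 1:1 allocation each arm has about 150/2 = 75. Then 0.5 ± 1.96 × √(0.25/75) = 0.5 ± 0.113, that is 0.39 to 0.61.

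**What the step measures respond to.** Let T be total steps per day, s the share taken in the device and D the days observed, and suppose both monitors count correctly. Then:
- cumulative device steps = T × s × D
- wrist-minus-foot gap = T × (1 − s) × D
- device steps per day = T × s
- ratio of device to total steps = s

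Only the last depends on s alone. If steps per day is taken from the wrist monitor it equals T and carries no information on adherence.

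**Illustrations.** The protocol gives no step counts, so T and s below are assumptions. D is 56 unless stated.

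1. Device steps and walking volume. 2,000 × 0.9 × 56 = 100,800; 8,000 × 0.4 × 56 = 179,200. The less adherent person scores higher. Per day the figures are 1,800 and 3,200, so steps per day does not cure this.
2. Gap and walking volume. 8,000 × 0.2 × 56 = 89,600; 2,000 × 0.5 × 56 = 56,000. The person at 50% shows the smaller gap and looks more compliant than the person at 80%.
3. Device steps and follow-up. At 4,000 steps a day, 90% worn and healed at week 3 gives 4,000 × 0.9 × 21 = 75,600; 40% worn for the full period gives 4,000 × 0.4 × 56 = 89,600. The order is reversed again.
4. Early healing at fixed adherence. At 4,000 steps a day and s = 0.8, 56 days give 179,200 device steps and a gap of 44,800; 28 days give 89,600 and 22,400. Both halve while the ratio stays 0.8. The first change reads as worse adherence, the second as better.
5. Boot effect on walking. If the boot cut walking by 30%, from 4,000 to 2,800 a day, at s = 0.8, device steps per day would fall from 3,200 to 2,240 and the daily gap from 800 to 560. Adherence has not changed.

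No precision can be computed for mean cumulative steps or the mean gap, because the protocol gives no mean or SD for steps.

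**The case against.** **Randomisation.** A reader might infer that the comparison between arms is confounded by how active participants are. The document does not support that. Allocation is randomised, so baseline walking volume adds variance and not bias. The plan also compares arm averages and does not rank individuals, so illustrations 1 to 3 show that the measure is poor but give no size of bias between arms. What stands is that randomisation does not balance what the device itself changes. Section 4.5.1 describes a brace that immobilises the ankle. Any effect on walking or on time to healing would move the averages at equal adherence. Whether the boot has such effects, and how large, is not known from the document.

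**Steps per day.** This comparison in 4.6.5 removes the dependence on days observed. That is right, so the follow-up problem belongs only to the cumulative measures. Dependence on walking volume remains.

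**The data are not lost.** A reader might infer that the objective cannot be answered. It can, because a ratio can be formed from the paired weekly readings. A statistical analysis plan might define one, but it would then depart from measures that 4.6.5 and 4.9 state outright, so the protocol text still needs correcting.

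**The 80% figure.** A reader might take this as the protocol's own criterion. It is not. Section 2.3 reports it from studies in high-income countries and warns that low- and middle-income settings may differ. It is useful only as a descriptive point of comparison, and an approximate one, since it refers to daily steps or time and the readings here are weekly.

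**Conclusion.** The point holds as an inconsistency with a practical consequence. The objective and the sample size concern an adherence rate; the stated analysis yields step counts and a raw step gap. All the device-based measures scale with walking volume. The cumulative ones also scale with observation time, where early healing pulls device steps and the gap in directions that contradict each other as signs of adherence.

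The interval in 4.4 is arithmetically correct, but it describes all 150 participants. A rate reported by arm rests on about 75 people, with an interval of 0.39 to 0.61 at 0.5.

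The reversals in the illustrations rest on assumed step counts and shares worn. They show what can happen; how often it would happen cannot be judged from the protocol. If the 70% control healing rate assumed in 4.4 refers to the 8-week period, most control participants would have shortened follow-up, so the dependence on days observed would not be a rare case.

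**What to change.** In sections 4.6.5 and 4.9:
- Define each participant's adherence as device steps divided by total steps over the same days, summed over the weeks in which both pedometers were read.
- Report the mean ratio in each arm and the difference between arms, with 95% CIs.
- Add the proportion with a ratio of at least 80%, with 95% CIs, as a descriptive summary for comparison with the literature in 2.3.
- Keep steps per day as a separate activity outcome, and name the pedometer it comes from.
- State that the control arm's foot pedometer sits in the MCR footwear. Section 4.6.5 places one only in the walker boot, although 4.9 needs a foot count in both arms.
- Fix one position for the second pedometer in both arms. Section 4.6.5 allows wrist or pocket, and Appendix 3 says in hand.

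In section 4.4, restate the precision for one arm of about 75: 0.39 to 0.61 at 0.5.

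The cost is mainly wording, with the same pedometers and the same weekly readings. There are two downsides. The stated interval becomes wider. The ratio may also carry some error, because foot and wrist monitors need not count alike even when the device is always worn. A short walk at fitting with both counts recorded would allow calibration, but it is optional: section 4.5.1 describes a supervised walk only for the boot arm, so it would be a new procedure for controls.

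### The QUEST satisfaction score is to be compared by an unadjusted t-test, which ignores the (unnamed) randomisation strata and conflicts with the stated preference for intervals over tests

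*Protocol*

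**What the plan says.** **Allocation (Protocol 4.6.3).** "Participants will be enrolled sequentially, and randomly allocated (1:1) to receive removable walker boot or MCR". On the sequence: "A permuted block random method will be used to generate the randomization sequence within each stratum". On the blocks: "Randomly selected blocks of size 2, 4, 6, or 8 will be generated to maintain balance between the numbers allocated". No stratification factor is named in this section or elsewhere in the protocol. Gender and age group appear as strata in section 4.8, but only for choosing interviewees.

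**Size (Protocol 4.4).** "We will include 150 people with neuropathic ulcers due to leprosy and diabetes in the study (75 each from India and Nepal").

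**Analysis (Protocol 4.9).** For satisfaction: "The mean user satisfaction score between the intervention and control group will be tested using t-test". For the step-count contrast: "We will also measure and compare the difference between wrist and foot between intervention and control", with no model named. For healing, the percentage reduction in ulcer area "will be compared between the two groups using methods we have used before". The paragraph closes by saying that the trial's philosophy rests on "confidence/credible intervals and not on hypothesis testing".

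**The concern.** Two things do not fit together.

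First, blocking within strata holds the arms close to balance on the strata, so differences between strata contribute almost nothing to the chance error of the between-arm difference. A two-sample t-test does not know this. Its standard error uses the total variance of the score, including the part that lies between strata. If that part is appreciable, the reported interval is wider than the design warrants, and some of the benefit of stratifying is lost.

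Second, the satisfaction outcome is to be tested, with no mean difference or interval specified for it, in a paragraph that says the trial does not rest on testing. An analyst following 4.9 literally would report a p-value where the stated philosophy calls for an estimate with its uncertainty.

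At stake is the precision and form of one of the three main results. Its validity is not in question.

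**Working it through.** **The plan's own figure.** The protocol gives no precision figure for satisfaction. Its only interval is for an adherence proportion of 0.5 with n = 150: 0.5 ± 1.96 × √(0.25/150) = 0.5 ± 0.080, or 0.420 to 0.580. This reproduces the 0.42 to 0.58 in section 4.4. It does not bear on the QUEST comparison.

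**Inputs for the check.**
- Total 150 (section 4.4) with 1:1 allocation (4.6.3), so about 75 per arm.
- Random block sizes 2, 4, 6 or 8 within strata (4.6.3).
- R², the share of QUEST score variance explained by the strata. The protocol gives neither this share nor the SD of the score. *Assumed range:* 0 to 0.30.
- Number of strata: not stated. *Assumed:* 2 or 4, for the simulation only.

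**Formulae.** Let σ² be the total variance of the score.
- Variance used by the t-test: σ² × (1/75 + 1/75).
- Actual variance of the difference when arms are balanced within strata: (1 − R²) × σ² × (1/75 + 1/75).
- Width of the unadjusted interval relative to the adjusted one: 1/√(1 − R²).
- Coverage of the nominal 95% unadjusted interval: 2Φ(1.96/√(1 − R²)) − 1.

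For example, at R² = 0.20 the width ratio is 1/√0.80 = 1.118, and the coverage is 2Φ(1.96 × 1.118) − 1 = 97.2%.

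| R² (assumed) | Width ratio | Extra width | Coverage, unadjusted | Type I error at nominal 5% |
|---|---|---|---|---|
| 0 | 1.000 | 0% | 95.0% | 5.0% |
| 0.05 | 1.026 | 3% | 95.6% | 4.4% |
| 0.10 | 1.054 | 5% | 96.1% | 3.9% |
| 0.20 | 1.118 | 12% | 97.2% | 2.8% |
| 0.30 | 1.195 | 20% | 98.1% | 1.9% |

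**Check by simulation.** N = 150, blocks of 2/4/6/8 within 2 or 4 strata, 10,000 runs per setting, comparing a pooled t-test with a linear model containing stratum terms.
- Width ratios were 1.00, 1.03, 1.05, 1.12 and 1.20 at R² = 0, 0.05, 0.10, 0.20 and 0.30, the same for 2 and 4 strata to two decimals.
- At R² = 0.20 the mean half-widths were 0.323 SD unadjusted and 0.288 SD adjusted.
- Coverage of the unadjusted interval was about 96%, 97% and 98% at R² = 0.10, 0.20 and 0.30. The adjusted interval stayed between 94.6% and 95.6% in all settings.
- At R² = 0 adjustment cost nothing visible (ratio 0.999 to 1.000).

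**The wording conflict.** This needs no arithmetic. The satisfaction sentence in 4.9 prescribes a test and no interval, while the last sentence of the same paragraph prescribes intervals and disclaims tests. Both cannot govern the QUEST result as written.

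**The case against.** The strongest reply has four parts.

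*Covariate adjustment is normally SAP material, and only the protocol was examined here.* This stands for steps and healing, where the protocol names no model. It does not stand for QUEST, because section 4.9 names a method and that method leaves the strata out.

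*The loss is assumed.* This stands. Nothing in the protocol shows that the strata predict satisfaction with a device. If they do not, nothing is lost, and if they explain 5% of the variance the interval is only about 3% wider.

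*The error is in the safe direction.* This also stands. The comparison is not biased by the stratification, coverage is at or above nominal, and no false claim of benefit follows. The precision on which section 4.4 sizes the trial is that of a single adherence proportion, which the t-test does not touch.

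*The conflict with the philosophy is a matter of one word,* because the same t procedure yields a mean difference and an interval. That makes it easy to resolve, but as written it is still a conflict.

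A reader might also infer that country and cause of ulcer are the strata, since recruitment differs between India and Nepal and the two diseases are pooled. The protocol does not say so, and they are only candidates. If the table was built on something else, variation between countries or causes has not necessarily been removed by design.

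**Conclusion.** The point holds for the QUEST satisfaction score. Section 4.9 fixes an analysis that ignores the randomisation strata of 4.6.3 and prescribes a test where the same paragraph disclaims testing. The consequence for the interval is conditional: unbiased, and between 0% and 20% wider than necessary over an assumed R² of 0 to 0.30. The size cannot be settled from the protocol.

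A reader might infer more: that every planned comparison in the trial is unadjusted, or that the intervals are certainly too wide. The document supports neither. The step-count comparison has no stated model, healing relies on unspecified prior methods, and excess width arises only if the strata predict the score. Leaving the strata unnamed would, taken alone, be missing detail. It matters here because the analysis cannot be matched to the allocation until the strata are known.

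**What to change.** 1. In 4.6.3, state the stratification factors actually used to generate the allocation table. These should be read from the table and not chosen afresh, since naming other factors would misdescribe the trial. If the table was not stratified, say so and remove the reference to strata.
2. In 4.9, replace the t-test for QUEST with a linear model containing arm and the randomisation strata, and report the adjusted mean difference with its 95% CI. This resolves both the mismatch with the design and the conflict with the stated philosophy.

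The cost is wording, with no extra participants or visits. The stratum for each participant should come from the randomisation record, because the data collection form in Appendix 3 has no explicit item for country or for cause of ulcer. With few strata the model costs almost nothing even if they turn out not to predict the score. No change to the adherence or healing analyses follows from this point.

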1.8 Outcomes

The main outcome measures are; 1) Adherence to removable walker boot which will be measured using pedometer; one placed inside the walker boot and second on patient's wrists as a watch/ in pocket. 2) User satisfaction which will be measured using standard questionnaire. 3) Ulcer healing which we will measure the healing of ulcer time to (complete epithelisation of ulcer) and measure the rate of healing both assessed from photographs by masked observers.

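### The fixed 8-week area-reduction metric in section 4.9 cannot tell early from late healing among ulcers that heal, so time to epithelisation should be the healing comparison

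*Protocol*

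**What the plan says.** Two healing outcomes are named. Section 1.8 says the trial will "measure the healing of ulcer time to (complete epithelisation of ulcer) and measure the rate of healing", and section 4.6.5 repeats both.

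The schedule in section 4.6.5 is that "photographs of ulcers will be taken at baseline and after every 2 weeks until the ulcer heals or at 8 weeks, whichever is earlier". Section 4.7 adds weekly follow-up that stops at healing or at 8 weeks. It also allows patients with complications that affect device wear, including worsening of the ulcer, to be treated as censored and followed no further.

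The analysis plan (section 4.9) states one healing contrast: "percentage reduction in the ulcer area per unit time (8 weeks) will be compared between the two groups", "using methods we have used before". It says that inference rests on "confidence/credible intervals and not on hypothesis testing".

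The sample size section (4.4) argues from "given a control healing rate of 70" per cent, against 90% in the intervention arm for 80% power, and does not expect to observe a difference. The ethics section that follows the Gantt chart expects the device to make ulcers heal faster.

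**The concern.** Photographs stop when the ulcer closes, and a closed ulcer has zero area. With the time unit fixed at 8 weeks, every ulcer healed by the end of follow-up gets the same score, whenever it closed. Yet speed is the benefit that the ethics section expects, and time to epithelisation is one of the two healing outcomes that sections 1.8 and 4.6.5 name. The term healing rate also changes meaning: in section 4.4 it reads as a proportion healed, and in section 4.9 it is an area reduction.

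What is at stake is the estimate passed to the next trial. The secondary objectives are to pilot trial methods and measurements and to observe healing in the two arms. A device that closed ulcers sooner without changing how many had closed by week 8 would appear to do nothing on the one stated contrast.

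**Working it through.** **Inputs from the protocol.** 150 patients, allocated 1:1, so 75 per arm (4.4, 4.6.3); healing rates of 70% and 90% (4.4, no time point given); photographs at weeks 2, 4, 6 and 8 or at healing (4.6.5, Appendix 3).

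**The plan's own figure.** For 70% v 90% with 75 per arm and two-sided 5% (assumed), power is 87.2% uncorrected, 82.3% with continuity correction and 83.7% by Fisher's exact test. With the correction, 89% healed gives 77.1%, so 90% is the smallest whole percentage that reaches 80%. The stated 90% reproduces and is not in dispute.

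**What the metric does with healing time.** Percentage reduction = 100 × (baseline area − final area) / baseline area.
- Closed at week 2: 100% per 8 weeks. Closed at week 8: 100% per 8 weeks. Difference 0.
- Divided by each ulcer's own elapsed time: 100/2 = 50% per week against 100/8 = 12.5% per week.

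**How many patients are at the ceiling.** If the section 4.4 rates apply at 8 weeks: 0.70 × 75 + 0.90 × 75 = 52.5 + 67.5 = 120 of 150.

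**Illustrative size of the loss.** These inputs are assumptions, not protocol figures: 75 per arm, two-weekly assessment, and unhealed ulcers reduced by 20% to 90% (uniform, mean 55%). The area metric is compared with mean time to healing capped at 8 weeks; entries are the share of simulated trials whose 95% interval excludes zero.

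| Scenario | Area reduction per 8 weeks | Capped time to healing |
|---|---|---|
| A. 80% healed in both arms; healing at weeks 2/4/6/8 of 10/15/25/30% v 30/25/15/10% | 5% (chance level) | 96% |
| B. Constant hazards giving 70% v 90% healed by week 8 | about 80% | 89% |
| C. Constant hazards giving 70% v 80% healed by week 8 | 23% to 25% | 28% |

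Hand check of A:
- Slow arm mean: 0.10×2 + 0.15×4 + 0.25×6 + 0.30×8 + 0.20×8 = 6.3 weeks. Fast arm mean: 0.30×2 + 0.25×4 + 0.15×6 + 0.10×8 + 0.20×8 = 4.9 weeks. Difference 1.4 weeks.
- Variances are 4.11 and 5.79, so SE = √((4.11 + 5.79)/75) = 0.36 and power ≈ Φ(1.4/0.363 − 1.96) = Φ(1.89) ≈ 97%.
- The mean area reduction is 0.80×100 + 0.20×55 = 91% in both arms, so its expected difference is 0.

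Hand check of B: moving 20% of patients from a mean of 55% to 100% shifts the mean area reduction by 0.20 × 45 = 9 points, which the metric does see.

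**Choice of replacement.** In a variant with 70% healed in both arms and mean healing time among healed ulcers of 6 v 4 weeks, the area metric was again null (4.5%). The log-rank test reached 39% and percentage per elapsed week 95%. With 70% v 90% healed and identical timing among healed ulcers, the area metric gave 82%, log-rank 78% and percentage per elapsed week only 35%. No single area-based rate serves both situations.

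**The case against.** Four points weigh on the other side.

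- **Silence on a survival model.** The sentence in section 4.9 concerns the healing rate, the second of the two named outcomes. Time to epithelisation may be analysed under a SAP that is not shown, or under the earlier methods to which the sentence refers; the censoring language in section 4.7 suggests as much. This stands. A reader might infer that the time outcome goes unused, but the protocol does not say so. The point rests on the metric that section 4.9 does fix.
- **Ambiguous denominator.** If per unit time meant each ulcer's own elapsed time, speed would be captured. The bracketed 8 weeks makes this the less natural reading, but it is possible. If it was intended, the wording still needs correcting.
- **Blind is too strong a word.** A reader might infer that the contrast cannot detect faster healing at all. That holds only where timing differs and the proportion healed does not, as in scenario A. Faster healing will often also raise the proportion healed by week 8, and then the loss is modest (B and C). This stands in full.
- **Limited consequence.** Healing is a secondary objective of a feasibility trial, no detectable difference is expected, and the dated measurements allow other endpoints to be derived later. This lowers the stakes. Relying on intervals instead of tests does not remove the problem, because the quantity being estimated itself leaves out speed among healed ulcers.

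**Conclusion.** The point holds in a limited form. As worded, the healing contrast in section 4.9 gives every ulcer healed by week 8 the same value and so discards timing among them: about 120 of 150 patients, if the section 4.4 rates are assumed to apply at 8 weeks. It keeps the information on whether ulcers healed by then and on the shrinkage of unhealed ones.

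The cost ranges from total (5% v 96%, arms differing in timing alone) to modest (about 80% v 89% at 70% v 90% healed; 23% to 25% v 28% at 70% v 80%). These figures depend on the assumed timing and on the assumed reduction in unhealed ulcers; the equal scoring of healed ulcers depends only on the fixed-window reading. The documents do not support the stronger conclusion that the pilot data would necessarily mislead. The amendment is worth making because the present wording does not match the trial's named outcome or its expected benefit.

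**What to change.** In section 4.9:

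1. Make time to complete epithelisation the healing comparison: Kaplan-Meier curves by arm and the difference in restricted mean time to healing over 8 weeks, with 95% CI. The restricted mean is preferable to a log-rank test alone, which lost much of the signal when the curves met at week 8.
2. Add the proportion healed at 8 weeks by arm and its difference, with 95% CI. This also ties the analysis to the 70% and 90% in section 4.4, whose time point should be stated.
3. Keep percentage area reduction as supportive only, either divided by each ulcer's own elapsed time or modelled from the two-weekly areas with adjustment for baseline area. State the denominator explicitly.
4. In the analysis, count patients taken off follow-up for worsening under section 4.7 as not healed by 8 weeks, or show this as a sensitivity analysis. Treating them as non-informatively censored would assume that they had the same healing prospects as those still followed.
5. Note that healing times are known only to the assessment interval.

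The cost is analysis wording. The case record form in Appendix 3 already has dates, photographs and ulcer dimensions at weeks 2, 4 and 6, and at week 8 or complete healing.
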